#### 4.2.7.2. Statistical Evaluation of Safety

Safety parameters that will be assessed include safety clinical laboratory parameters, vital signs, and ECG parameters. The parameters will be listed and summarized using standard descriptive statistics. Additional analysis will be performed if warranted upon review of the data.

A shift table for each IV dose will be constructed to assess the MRI measurement pre- and postdose for changes and additions of vasogenic edema and microhemorrhages (ARIA-E and ARIA-H)

Suicide-related thoughts and behaviors based on the C-SSRS will be listed by patient. Only time points and patients that show ideation/behavior of suicide will be displayed (ie, all “no” responses may not be displayed).

Exploratory analyses of Fridericia's corrected QT interval (QTcF) data from ECG monitoring in a Phase 1 trial are performed to judge the extent and/or risk of QT prolongation. There will be an exploratory assessment of potential prolongation by examining mean change in QTcF as a function of serum drug concentration obtained and an inspection of the upper confidence limit relative to a value of 10 msec, which is consistent with International Conference on Harmonisation (ICH) guidance. Frequency tables of QTc changes from baseline and large QTc values may also be obtained in accordance with ICH guidance.

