5.2. Rationale and Justification for the Study

This is the second study with LY3002813 in patients with MCI due to AD or mild to moderate AD. Data from Study AACC indicated a dramatic reduction in cerebral amyloid (as assessed by florbetapir PET imaging) in the 6 patients who received 3 to 5 doses of 10 mg/kg of LY3002813 IV over 6 months, without cerebral vasogenic edema or microhemorrhage complications in this dose group. These positive results were accompanied by a high incidence of ADAs at all doses, as well as infusion reactions noted at doses ≤ 3 mg/kg. Dosing was stopped in the multiple-dose phase of Phase 1 Study I5T-MC-AACC (Study AACC) due to high prevalence of ADAs and unexpected rapid clearance of the study drug.

As a result of the significant target engagement (amyloid reduction by florbetapir PET) that was identified after 3 to 5 doses of LY3002813 10 mg/kg IV over 6 months, the current study is proposed to determine whether different dosing regimens (single-dose, short-term “induction” dosing with higher, more frequent dosing; and chronic dosing for maximal PD effect) can mitigate immunogenicity and immune safety issues, and produce sustained amyloid reduction. The aims of the study are to evaluate the effect of different dosing regimens on ADAs and amyloid plaque removal, and assess the relationship between PK, PD (amyloid removal), immunogenicity, and clinical safety. As a high prevalence of ADAs was observed in Study AACC, a risk management plan for immune safety will be incorporated into the clinical trial including at least 6 hours monitoring after completion of each infusion, a protocol for management of infusion reactions, and standardized data collection for infusion reaction AEs.

A favorable risk/benefit profile and dosing selection will support further development of LY3002813, including: (1) removal of amyloid consistent with Study AACC; (2) persistence of amyloid removal after completion of dosing; (3) acceptable clinical impact of ADAs; (4) manageable risk of clinically significant infusion reactions; and (5) low incidence of amyloid-related imaging abnormalities-edema (ARIA-E) and ARIA-H.

6. Objectives

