- [28] have current serious or unstable illnesses including hepatic disease (cirrhosis, hepatitis A, B, or C [presence of antibody to hepatitis B surface antigen in the setting of hepatitis B immunization is not an exclusion; the presence of hepatitis C antibody a normal liver function tests and a negative hepatitis C polymerase chain reaction is also not an exclusion]); renal, gastroenterologic, respiratory, cardiovascular disease (active ischemic heart disease [stable or unstable angina], intermittent atrial fibrillation); endocrinologic disease (stable non-insulin-dependent diabetes or stable thyroid disease is not an exclusion); neurologic disease (other than AD); psychiatric disease (including suicidal ideation); immunologic, infectious (HIV, tuberculosis, Lyme, or hematologic disease (including transfusion within past year), or other conditions that, in the investigator's opinion, could interfere with the analyses of safety in this study.
- [29] have a history of uncontrolled asthma, significant autoimmune disease (rheumatoid arthritis, systematic lupus erythematosus), hereditary angioedema, or common variable immune deficiency

- [30] have any contraindications for MRI, including claustrophobia or the presence of contraindicated metal (ferromagnetic) implants/cardiac pacemaker
- [31] have a head MRI (central read) demonstrating either greater than 4 cerebral microhemorrhages on T₂*-weighted gradient-echo sequence (regardless of their anatomical location), or a single area of superficial siderosis, or prior evidence of macrohemorrhage, or any other major intracranial pathology except: atrophy, meningiomas without mass effect, benign pituitary microadenomas, and/or mild to moderate white matter hyperintensities on fluid attenuation inversion recovery (FLAIR)
- [32] have a history of intracranial hemorrhage; cerebrovascular aneurysm or arteriovenous malformation; or carotid artery occlusion, stroke, or epilepsy

Exclusion criteria [33] to [36] only apply to patients who will require an LP during the study:

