 - Lilly stops the study or stops the patient's participation in the study for medical, safety, regulatory, or other reasons consistent with applicable laws, regulations, and good clinical practice (GCP)
- AE
 - if a clinically significant event (CSE) occurs, the investigational product is to be discontinued and appropriate measures taken. Lilly or its designee should be alerted immediately. A CSE will be defined as a moderate to severe AE, abnormal clinical sign, or clinical laboratory finding that may pose a risk to the well-being of the patient. Refer to Section 10.6.
 - a clinically significant systemic hypersensitivity reaction occurs following administration of the LY3002813 (for example, drug-related symptomatic bronchospasm, allergy-related edema/angioedema, or hypotension), that requires parenteral medication, does not respond to symptomatic medication, or results in clinical sequelae or an anaphylactic reaction
 - Appearance of clinically significant new cerebral ischemic or hemorrhagic events by MRI, as judged by the investigator and agreed by the clinical pharmacologist/CRP
 - Appearance of symptomatic or asymptomatic ARIA-E (also known as cerebral vasogenic edema)
 - Appearance of symptomatic ARIA-H, including superficial siderosis, or an asymptomatic increase in the number of cerebral microhemorrhages >4 over baseline

Where possible, subjects who discontinue the investigational product because of an AE will continue with safety, PK, PD, and other assessments as per protocol and as deemed appropriate by the investigator and the Lilly clinical pharmacologist/CRP.

8.2.1.3. Suspension or Termination of Dosing for Either Dose Escalation or within a Dose Cohort

Dosing within a cohort, or dose escalation to a higher dose cohort (Cohorts 3, 5, 7), may be suspended or terminated if any of the following scenarios occur within a given dose cohort as determined by the unblinded Lilly CRP or clinical pharmacologist:

- 1) ≥ 2 patients experience an SAE that is considered related to LY3002813 administration. This would include:
 - a) signs and/or symptoms consistent with meningoencephalitis
 - b) fixed-focal neurological deficit
- 2) ≥ 2 patients experience evidence of clinically significant new cerebral ischemic or hemorrhagic events by MRI, as judged by the investigator and agreed by the clinical pharmacologist/CRP
- 3) ≥ 2 patients experience asymptomatic or symptomatic ARIA-E

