- 4) ≥ 2 patients experience symptomatic ARIA-H, including superficial siderosis, or an asymptomatic increase in the number of cerebral microhemorrhages >4 over baseline
- 5) ≥ 2 patients develop clinically significant acute infusion AEs considered related to LY3002813 during or within 6 hours of completing the infusion that do not resolve with a reduced infusion rate and/or supportive care
- 6) ≥ 2 patients experience similar CSEs considered related to LY3002813. A CSE will be defined as a moderate to severe AE, abnormal clinical sign, or clinical laboratory finding that may pose a risk to the well-being of the patient.
- 7) 50% or more patients at a dose level experience moderate or severe AEs that impair normal activities, but do not meet the CSE criteria, and are considered related to study treatment
- 8) If an SAE occurs during the infusion of the study drug, irrespective of causality, the drug is discontinued immediately. No redosing or completion of dosing is considered for that patient. If the infusion SAE is considered related to LY3002813, then the remaining cohort is not dosed.

It is important to note that when the above criteria are met, the dosing at the same and higher dose levels may be suspended or terminated, but any ongoing dose level that is below the dose that triggered the stopping rule may continue when considered appropriate by the sponsor.

Any cohort that has been suspended may be re-initiated at a later date if a review of all available safety data by the sponsor supports this action. The decision to re-initiate the cohort, together with the supporting safety data, will be documented and shared with the investigators, institutional review board, and regulatory agencies, as appropriate. If multiple dose levels are involved, the original dose-escalation plans will be adhered to.

In the event of an SAE that is related to the investigational product, other than precautionary inpatient observation, dosing may be suspended, for that cohort and/or higher cohorts.

Refer to the Study Schedule ([Attachment 1](#)) for data collected at the time of discontinuation and follow-up.

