11.2.7.2. Statistical Evaluation of Safety

Safety parameters that will be assessed include safety laboratory parameters, vital signs, and ECG parameters. The parameters will be listed and summarized using standard descriptive statistics. Additional analysis will be performed if warranted upon review of the data.

A shift table for each dose group will be constructed to assess the MRI measurement pre- and postdose for changes and additions of vasogenic edema and microhemorrhages.

Suicide-related thoughts and behaviors based on the C-SSRS will be listed by patient. Only time points and patients that show ideation/behavior of suicide will be displayed (ie, all “no” responses will not be displayed).

Exploratory analyses of Fridericia’s corrected QT interval data from ECG monitoring in a Phase 1 trial are performed to judge the extent and/or risk of QT prolongation. There will be an exploratory assessment of potential prolongation by examining mean change in Fridericia’s corrected QT interval as a function of serum drug concentration obtained and an inspection of the upper confidence limit relative to a value of 10 msec, which is consistent with International Conference on Harmonisation (ICH) guidance. Frequency tables of QTc changes from baseline and large QTc values may also be obtained in accordance with ICH guidance.

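### The ARIA shift table counts only microhemorrhages as ARIA-H, while the symptomatic ARIA-H discontinuation and suspension rules also count superficial siderosis

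*SAP*

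**What the plan says.** **The analysis.** SAP Section 4.2.7.2 plans a pre- to postdose MRI shift table for each IV dose, covering "changes and additions of vasogenic edema and microhemorrhages (ARIA-E and ARIA-H"). Protocol Section 11.2.7.2 plans the same table for "changes and additions of vasogenic edema and microhemorrhages", without the ARIA labels. No other table in either document is specific to ARIA.

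**The rules.** Protocol Section 8.2.1.2 discontinues a patient on "Appearance of symptomatic ARIA-H, including superficial siderosis, or an asymptomatic increase in the number of cerebral microhemorrhages >4 over baseline". Item 4 of Section 8.2.1.3 uses the same wording at cohort level, once at least 2 patients are affected.

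**Other uses of the term.** The protocol's abbreviation list expands ARIA-H as microhemorrhage alone. Section 10.6.3.7 pairs ARIA-E and ARIA-H with vasogenic edema and microhemorrhage. SAP Section 4.2.3 puts a third label, ARIA-M, in the baseline table without defining it.

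**Siderosis elsewhere.** Exclusion criterion [31] bars patients whose centrally read screening MRI shows more than 4 microhemorrhages "or a single area of superficial siderosis". In the SAP, superficial siderosis appears only in its copy of that criterion.

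**Use of the result.** Protocol Section 5.2 lists five features that would support further development. The fifth is "low incidence of amyloid-related imaging abnormalities-edema (ARIA-E) and ARIA-H".

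**The concern.** ARIA-H carries two meanings. For stopping treatment it includes superficial siderosis when the ARIA-H is symptomatic. For the table that summarizes ARIA by dose it means microhemorrhage. Neither document reconciles the two or says how siderosis arising on study is tabulated. A programmer following SAP Section 4.2.7.2, with the abbreviation list at hand, would have no reason to add a siderosis row.

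What is at stake is the ARIA-H incidence by dose, which Section 5.2 makes a condition for going forward. Measured against the usage in the stopping rules, the tabulated count in any group can be too low but never too high. In an extreme case, a cohort could be suspended for ARIA-H that its own ARIA table does not show.

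**Working it through.** The plan states no figure to reproduce. The check is a comparison of texts, followed by simple proportions.

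**Step 1: what each place counts as ARIA-H.**

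- SAP 4.2.7.2: microhemorrhages, labelled ARIA-H.
- Protocol 11.2.7.2: microhemorrhages, no label.
- Protocol abbreviation list and Section 10.6.3.7: microhemorrhage.
- Protocol 8.2.1.2 and 8.2.1.3 item 4, symptomatic limb: ARIA-H with superficial siderosis included.
- The same two rules, asymptomatic limb: an increase of more than 4 microhemorrhages over baseline; siderosis not named.

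Both meanings stand in the current protocol. The conflict is therefore not merely the result of a SAP approved in December 2015 being read beside a protocol amendment approved in December 2017.

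**Step 2: two kinds of patient with new siderosis and no new microhemorrhage.**

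- *Symptomatic.* ARIA-H under both rules. No shift in the table as described. Present in the adverse event output (Protocol 10.6.1, SAP 4.2.7.1) and, if discontinued, in the reported reasons where known (Protocol 11.2.2, SAP 4.2.2).
- *Asymptomatic.* Not ARIA-H under either limb of the rules. No shift in the table. An adverse event is expected where a clinically significant MRI finding leads to a diagnosis (Protocol 10.6.1). The general adverse event definition might also apply, but that rests on the investigator's judgement.

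**Step 3: size per patient.** The inputs are the planned active patients: 6 in each of Cohorts 1 to 3 and 9 in each of Cohorts 4 to 7 (Protocol 7.1.3 to 7.1.5 and 11.1). The understatement of a dose group's ARIA-H proportion is k/n, where k is the number of omitted patients and n the number of active patients.

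- One patient, single dose: 1/6 = 16.7 percentage points.
- One patient, multiple dose: 1/9 = 11.1 percentage points.

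**Step 4: the cohort rule.** Suppose two active patients in one cohort have symptomatic siderosis, no microhemorrhage change, and no other patient has ARIA-H. Item 4 of Section 8.2.1.3 is met. Under the rule's usage the rate is 2/6 = 33.3% or 2/9 = 22.2%. The shift table, read literally, shows 0/6 or 0/9.

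**Step 5: probability.** This needs a siderosis rate, or an ARIA-H rate and the share that is siderosis only. The documents give none of these, so no probability is calculated.

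**The case against.** The strongest reply is that these patients are not lost. Symptoms after dosing are adverse events, which must be reported, are listed, and are presented by dose and severity. Discontinuations are reported with their reasons. SAP Section 4.2.7.1 promises a descriptive summary of all safety data, the protocol synopsis lists MRI scans as a safety parameter, and the interim safety reviews in Protocol Section 11.3 include imaging. This stands for the symptomatic patient. A reader might infer that siderosis-only patients drop out of the safety results altogether; the documents do not support that. What remains is that a listing is not an ARIA-H incidence by dose, and a general promise to summarize neither defines ARIA-H nor creates a siderosis row.

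A reader might also infer that any superficial siderosis is ARIA-H for stopping. That goes too far. Both rules name siderosis only in the symptomatic limb. Asymptomatic siderosis alone could trigger action only through the separate criterion on clinically significant new hemorrhagic events by MRI, which is a judgement and is not labelled ARIA-H.

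The duty to report adverse events is also wider than findings that lead to a diagnosis: all adverse events after the first dose must be reported, and the definition includes unfavorable and unintended signs. A new asymptomatic siderosis may therefore be captured. It is not assured, but it would be wrong to say that it will be missed.

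Finally, the SAP's parenthetical label could be taken to cover all ARIA-H. The wording attaches the labels to the two findings just named, and the abbreviation list and Section 10.6.3.7 favor the narrow reading.

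**Conclusion.** The point holds for the ARIA shift table. A patient with symptomatic superficial siderosis and no new microhemorrhage is ARIA-H under the discontinuation and suspension rules but changes nothing in the only ARIA-specific table. Each such active patient lowers the tabulated ARIA-H rate by 16.7 points in a single-dose group or 11.1 points in a multiple-dose group.

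This assumes the planned group sizes and a literal reading of the table description. How often it would occur is unknown. The certain direction applies to the count within a group, not to the difference from placebo, since a placebo patient could be omitted in the same way.

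It is a reporting inconsistency that should be corrected before the safety tables are produced, because ARIA-H incidence feeds a stated development criterion. It does not show that safety events would go unreported, and it takes no position on which stopping criterion is right.

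**What to change.** - In SAP Section 4.2.7.2 and Protocol Section 11.2.7.2, define ARIA-H for reporting as new or increased microhemorrhages and/or new or increased superficial siderosis.
- Give the shift table three ARIA-H rows by dose: microhemorrhage, superficial siderosis, and any ARIA-H.
- Judge change against each patient's own baseline MRI. Criterion [31] should exclude siderosis at entry, but Protocol Section 8.2.1.1 lets inadvertently enrolled patients continue, so it is unsafe to assume that every postdose siderosis is new.
- Reconcile the ARIA-H wording in the abbreviation list and Protocol Section 10.6.3.7 with Sections 8.2.1.2 and 8.2.1.3, leaving every stopping rule as it is.
- Replace or define ARIA-M in SAP Section 4.2.3.

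The cost is small: two more table rows and a siderosis item in the read of the safety MRIs. Gradient-echo imaging and central reading are already planned, and siderosis is already part of the screening criterion. However, Section 10.6.3.7 mentions only microhemorrhages and vasogenic edema for the safety scans, so siderosis may have to be added to the read form, and scans already read may need another look. The reported ARIA-H rate may become less favorable.

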#### 4.2.7.3. Evaluation of Immunogenicity (for Large Molecules)

As part of the secondary study objective, Antibody drug formation will be summarized over time for each IV dose group. An MMRM will be done fitting IV dose, study visit, and interaction between study visit and dose as fixed effects and the dependent variable as the change from baseline in antibody formulation following dosing of LY3002813. The relationship between the presence, absence or level of ADAs and number of IV drug infusion reaction AEs, PK estimates of exposure, PD measurements of amyloid SUVR. These associations may be assessed using simple pairwise correlations and pairwise graphical relationship. These relationships may also be described using a modeling approach, if appropriate.

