Study Design: This is a 3-part, patient- and investigator-blind, randomized within cohort, placebo-controlled, parallel-group, single- and multiple-dose study in patients with MCI due to AD or mild to moderate AD to assess the safety, tolerability, PK, and PD of single and multiple IV doses of LY3002813. The study will be conducted in at least 7 cohorts. 
 Cohort 1: 10 mg/kg IV single dose Cohort 2: 20 mg/kg IV single dose Cohort 3: 40 mg/kg IV single dose Cohort 4: 10 mg/kg IV Q2W for 24 weeks Cohort 5: 20 mg/kg IV Q2W for 24 weeks Cohort 6: 10 mg/kg IV Q4W for up to 72 weeks Cohort 7: 20 mg/kg IV Q4W for up to 72 weeks 	

Each cohort will contain approximately 6 (single dose) or 9 (multiple dose) patients treated with LY3002813 and 2 to 3 patients treated with placebo so that the study can detect target engagement and antidrug antibody (ADA) frequency relative to those observed in Study I5T-MC-AACC.

Diagnosis and Main Criteria for Inclusion and Exclusion:

The study will enroll men or nonfertile women, at least 50 years of age with evidence of memory impairment on the Free and Cued Selective Reminding Test with Immediate Recall (FCSRT-IR), a Mini-Mental State Examination (MMSE) 16 to 30, a Clinical Dementia Rating of 0.5 to 2 and memory box score ≥ 0.5 , no history of macrohemorrhage and no more than 4 microhemorrhages on MRI, and a positive amyloid scan by florbetapir. Patients with contraindication for MRI, presence of >4 microhemorrhages on MRI, or history or evidence on MRI of macrohemorrhage will be excluded. Criteria for Japanese patients: Japanese if recruited at sites in Japan or up to third-generation Japanese if recruited at sites outside of Japan. “Third-generation Japanese” is defined as a patient whose biological grandparents are of exclusive Japanese descent and were born in Japan.

Investigational Product, Dosage, and Mode of Administration:

LY3002813, single and multiple doses, from 10 mg/kg up to 40 mg/kg, IV infusion

Comparator, Dose, and Mode of Administration:

Placebo (saline), IV infusion

Planned Duration of Treatment:

Part A (Cohorts 1, 2, and 3): single dose of LY3002813 or placebo followed by 72 weeks (for Cohorts 1 and 2) and 24 weeks (for Cohort 3) follow-up for each dose level

Part B (Cohorts 4 and 5): 13 doses of LY3002813 or placebo administered Q2W for 24 weeks followed by 48-weeks follow-up

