In the SAD portion of Study AACC, it was observed that LY3002813 had a significantly shorter half-life than the approximately 24-day half-life predicted based on data from nonclinical studies (a prediction that was consistent with the expected half-life of an immunoglobulin G1 antibody [Lobo et al. 2004]). After single-dose administration from 0.1 mg/kg to 3.0 mg/kg, the mean terminal elimination half-life was approximately 4 days, increasing to approximately 10 days (243 hours) at the 10-mg/kg dose level. The PK of a single dose of 1.0 mg/kg IV LY3002813 in young, healthy subjects was indistinguishable from the PK in AD patients at the same dose level. In the MAD phase, most patients at dose levels \leq 3 mg/kg had serum LY3002813 concentrations below the limits of detection 28 days after dosing; patients receiving 10 mg/kg did have sustained quantifiable concentrations 28 days after dosing.

Greater than 90% of the patients with AD had treatment-emergent antidrug antibodies (ADAs) 3 months after the first dose at all dose groups; titers tended to increase by the end of the MAD phase and persist 3 months after the last dose. Dosing was stopped in the MAD phase of Study AACC because of high prevalence of ADAs and unexpected rapid elimination of the study drug.

Sixteen adverse events (AEs) of mild or moderate infusion related reactions were reported in 6 of 51 patients dosed with LY3002813. Infusion reactions occurred in 1 patient in the 0.3-mg/kg cohort, 2 patients in the 1.0-mg/kg cohort, and 3 patients in the 3.0-mg/kg cohort. The infusion reactions developed in 1 of the 6 patients after the first MAD dose and in 5 of the 6 patients after the second MAD dose. One patient discontinued because of dyspnea due to an infusion reaction (mild severity). All patients with infusion reactions had high peak titers of ADAs. Three patients were rechallenged with premedication (acetaminophen, antihistamine, and/or hydrocortisone) and had milder reactions on rechallenge. Infusion reactions began during the infusion or within 30 minutes of completing the infusion and lasted between 1 minute and 8 hours. Symptoms included chills/shivering (3 patients); flushing (2 patients); hypotension (asymptomatic, 1 patient); dyspnea (1 patient); myalgia (1 patient); rash (1 patient); and fever (1 patient).

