9.5.1. Special Treatment Considerations

9.5.1.1. Premedication for Infusions

Premedication for dosing is not planned. However, if an infusion reaction occurs, appropriate medication may be used as determined by the study investigators (see Section 9.7). The patient may be premedicated for subsequent infusions. If infusion reactions are observed, but review of the data suggests that dosing may continue, administration of acetaminophen (500 to 1000 mg) and/or an antihistamine, and/or methylprednisolone (or other corticosteroid) may be administered orally 30 to 60 minutes before starting the infusion for subsequent patients.

The decision to implement premedication for infusions in subsequent cohorts will be made by the investigator and sponsor, and it will be recorded in the study documentation, along with the dose-escalation decision.

Any premedication given will be documented as a concomitant therapy (see Section 9.7).

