### **4.2.6. Pharmacokinetic/Pharmacodynamic Analyses**

Exploratory correlational analyzes may be conducted to describe the relationship between exposure and changes in the florbetapir SUVr; MRI of whole brain, ventricle, and hippocampus volumes; CSF concentrations of abeta, tau and ptau; maximum ADA levels; and number AEs related to infusion reactions. It is intended that these analyses will be descriptive graphs in nature as a function of LY3002813 dose, exposure, and/or time from study entry; however, the relationship may also be described using a modeling approach, if appropriate.

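### The ADA and infusion-reaction association uses a raw AE count with no denominator or stratification, although patients are planned to receive 1, 13 or 19 infusions

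*SAP*

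**What the plan says.** SAP 4.2.7.3 covers "The relationship between the presence, absence or level of ADAs and number of IV drug infusion reaction AEs", among other variables. On method it says: "These associations may be assessed using simple pairwise correlations and pairwise graphical relationship". It adds: "These relationships may also be described using a modeling approach, if appropriate". Nothing is said about infusions received, study Part, whether the ADA sample precedes the reaction, or patients who are premedicated, stopped or switched to placebo infusions.

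SAP 4.2.6 uses the same raw count in a different relation. It relates drug exposure to a list of outcomes that includes "maximum ADA levels; and number AEs related to infusion reactions".

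The opportunity to react differs by design. The Protocol synopsis gives "Part A (Cohorts 1, 2, and 3): single dose of LY3002813 or placebo followed by 72 weeks" for Cohorts 1 and 2 (24 weeks for Cohort 3), then 13 doses in Part B and 19 in Part C. Protocol 7.1.5 moves a Part C patient to placebo infusions after two consecutive scans with SUVr below 1.1.

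After a reaction, Protocol 9.5.1.1 states: "The patient may be premedicated for subsequent infusions". It also allows premedication to be introduced for later patients or cohorts. Under Protocol 9.5.1.2 a stopped infusion is not resumed, and Protocol 8.2.1.2 lists a clinically significant systemic hypersensitivity reaction as a ground for discontinuation.

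**The concern.** A count with no denominator rises with the number of chances to react. ADA may also differ by Part, since the regimens differ in length and frequency. A correlation across Parts can then arise because both variables follow the regimen.

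Protocol 5.1 makes this plausible. In Study AACC, where the same patients had a single dose and then multiple doses, titres tended to rise by the end of the multiple-dose phase. Reactions "developed in 1 of the 6 patients after the first MAD dose and in 5 of the 6 patients after the second MAD dose". Part A here has one infusion, so a patient can develop a high titre afterwards with no further infusion at which to react.

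Reactors can also be premedicated or stopped, which shortens or softens their later count. Protocol 5.1 reports: "Three patients were rechallenged with premedication (acetaminophen, antihistamine, and/or hydrocortisone) and had milder reactions on rechallenge".

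The ADA and reaction relation belongs to an exploratory objective (Protocol 6.3), and Protocol 5.2 names an acceptable clinical impact of ADAs as a criterion for further development. A misleading association in either direction would bear on that judgement.

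**Working it through.** **1. Infusions per patient.** From the schedule days in Protocol Attachment 1: Part B (169 − 1)/14 + 1 = 13; Part C (505 − 1)/28 + 1 = 19; Part A 1. The stated figures are reproduced.

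**2. Share of patients and infusions.** Planned active patients (Protocol 11.1): Part A 3 × 6 = 18; Part B 2 × 9 = 18; Part C 2 × 9 = 18; total 54. Planned active infusions: 18 × 1 = 18; 18 × 13 = 234; 18 × 19 = 342; total 594. Part A holds 18/54 = 33% of the patients and 18/594 = 3% of the infusions.

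**3. Counts at equal risk.** With risk p per infusion and n infusions, the expected count is np and P(at least one) = 1 − (1 − p)^n. The documents give no p, so a range is shown.

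| p (assumed) | Expected count, A / B / C | P(at least one), A / B / C |
|---|---|---|
| 1% | 0.01 / 0.13 / 0.19 | 1% / 12% / 17% |
| 5% | 0.05 / 0.65 / 0.95 | 5% / 49% / 62% |

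**4. AEs are not reactions.** Study AACC had 16 infusion-reaction AEs in 6 of 51 patients, or 16/6 = 2.67 per reactor. The Protocol does not separate repeat reactions from several AE terms for one reaction.

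**5. No true link, first model.** Simulated trials with 54 active patients, titre SD 2 log2, no reaction risk at the first infusion and equal risk at each repeat infusion. The test is a Spearman correlation of titre with raw count across Parts, at 5%. All inputs are assumptions.

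| Risk per repeat infusion | Titre in Parts B and C versus A | Mean correlation | Positive tests |
|---|---|---|---|
| 4% | no difference | about 0 | about 5% |
| 4% | 1 log2 higher | 0.11 | 11% |
| 4% | 2 log2 higher | 0.20 | 29–30% |
| 4% | 1 log2 lower | −0.10 | sign reversed |
| 1% | 1 or 2 log2 higher | small | about 5–8% |

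A within-Part correlation of titre with reactions per infusion gives about 5% positive tests at 4% risk with titres 1 or 2 log2 higher.

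**6. No true link, second model.** Equal risk at every infusion, with ADA rising by a fixed step from one Part to the next. For a step of 0.5 SD, the raw count is positive in 12–15% of trials at 2% risk and 26–27% at 5% risk. For a step of 1 SD it is 28–30% and 63–66%. With no step it is 4–5%. The within-Part rate stays at 4.4–6.6% throughout.

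**7. True link, titres equal across Parts.** The odds of reaction double per SD of ADA.

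| Risk | Handling of reactors | Raw count: correlation, detection | Within-Part rate: correlation, detection |
|---|---|---|---|
| 5% | none | 0.34, 73% | 0.40, 87% |
| 5% | half stopped, premedication halves risk | 0.31, 65% | 0.35, 73% |
| 5% | all stopped | 0.30, 61% | 0.34, 73% |
| 2% | any of these | 0.26, 49–51% | 0.27–0.28, 50–54% |

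Unequal infusion numbers dilute a real link. Premedication and stopping attenuate it modestly at 5% risk and hardly at all at 2%. If titres also rise by Part, the raw count detects more often (87% against 63% at 2% risk and a 0.5 SD step, no stopping). Part of that is the between-Part component of step 6, so it is not a gain.

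**Limit of the check.** Each simulated patient had one fixed titre. Pairing a titre with each infusion was not simulated.

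**The case against.** The strongest reply is that the SAP commits to very little. Correlations are optional, graphs and a model are allowed, and the text specifies neither pooling across Parts nor a Spearman test at 5%. That stands. The false-positive figures apply only if the association is taken across Parts, which the text permits and which 6 to 9 active patients per cohort make likely.

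A reader might infer several stronger things that the documents do not support:

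- **That the count measures infusions and rescue and not ADA.** It mixes all three. All AACC reactors had high peak titres, and step 7 shows that the raw count still carries a real ADA effect.
- **That the bias must inflate the link.** Protocol 7.2 and 9.3 expect that higher, more frequent dosing may reduce immunogenicity. Lower titres in Parts B and C reverse the sign, and equal titres remove the spurious association.
- **That Part A patients must score zero.** This extrapolates from 6 reactors at 0.3 to 3 mg/kg. Protocol 10.4.1 allows for ADA already present at baseline, and Protocol 9.5.1.2 recognises a reaction risk with any biological agent. Part A adds little information, which is not the same as none.
- **That SAP 4.2.6 correlates maximum ADA with reactions.** Both are separate outcomes related to exposure.
- **That this correlation is the main evidence on whether regimens mitigate immune problems.** That comparison rests on ADA by dose group over time (SAP 4.2.7.3) and AE incidence by dose (SAP 4.2.7.1).

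Reaction risk may also be low: Protocol 7.2 reports no infusion reactions in the AACC 10 mg/kg cohort, and at 1% risk the effect is small.

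**Conclusion.** The point holds as a defect of specification in an optional, exploratory analysis. The outcome named is a raw AE count, opportunity differs 1 : 13 : 19, and nothing in the SAP separates infusion number from ADA. Taken across Parts, the correlation can be spurious in either direction when titres differ by Part: about 11–30% positive tests at 4% risk per repeat infusion and a 1 to 2 log2 shift. It is diluted when titres do not differ (73% against 87% detection at 5% risk). Infusion number is the main problem, and premedication and stopping are secondary. The per-infusion risk, the titre differences and the strength of the link are assumptions; the infusion numbers, cohort sizes and missing denominator come from the documents. The change is worth making because it costs almost nothing.

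**What to change.** In SAP 4.2.7.3:

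- Carry out the ADA and infusion-reaction association in LY3002813-treated patients of Parts B and C, stratified by Part, and label it exploratory.
- Replace the raw AE count with reactions (several AE terms at one infusion counting once) per active infusion received, or with infusion number to first reaction.
- Pair each infusion with the most recent ADA titre drawn before it, by the same rule for reactors and non-reactors. A rule that measures reactors early and non-reactors at their final titre creates its own bias. With no true link, 4% risk and titres rising 1 or 2 log2 over dosing, it gives a mean correlation of −0.13 or −0.24 and 12% or 29% positive tests.
- Censor or flag at the first premedicated infusion, discontinuation, or switch to placebo infusions.
- Tabulate reactions per infusion by cohort, with and without premedication. Report Part A descriptively.

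In SAP 4.2.6, relate exposure to the per-infusion rate within Part.

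The cost is SAP wording. Dose times (Protocol 9.2), premedication (9.5.1.1, 9.7) and ADA samples (10.4) are already collected. The association uses 18 + 18 = 36 rather than 54 active patients, and the 18 left out add little to it. Titres will sometimes be carried forward: Protocol Attachment 3 allows at most 10 immunogenicity samples in Part B and 12 in Part C, against 13 and 19 infusions.
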